7.9.2. Secondary objectives

7.9.2.1. Secondary objective #1

This objective is to assess the reduction in number of voids per day from baseline following 12 PTNM therapy sessions.

Endpoint definition

The average number of voids per day collected from baseline and following the 12th PTNM therapy session will be used for analysis of this objective. Average voids per day will be calculated by summing all reported voids and dividing by the total number diary days. For a diary to be included in the analysis, it needs to have complete leak and/or void episode entries for at least one day. For any reported episode if leak or void is not indicated, the diary of that day will not be included.

Data collection and analysis methods

Diary data from both baseline and following the 12th PTNM therapy session will be included in the analysis. Reduction in average voids per day from baseline will be calculated for each subject at 12th PTNM. A paired t-test or the Wilcoxon signed-rank test will be used to evaluate the changes after 12th PTNM therapy session from baseline after testing for data normality by calculating Shapiro-Wilk W statistic.

Determination of subjects for analysis

This objective will be assessed in qualified subjects with ≥ 8 voids per day at baseline, who has diary data at both baseline and 12th PTNM session.

In addition to the primary analysis which includes subjects with diary data from baseline and 12th PTNM therapy session, the same sensitivity analyses as described in the primary objective will be performed for secondary objective #1.

Besides PTNM session 12, diary data are also collected for PTNM Session #1, #4, and #8. Reduction in number of voids per day from baseline will also be summarized by the PTNM session (session #1, #4, #8 and #12) when the diary data is collected.

7.9.2.2. Secondary objective #2

This objective is to assess the change from baseline through 12 PTNM therapy sessions in quality of life as measured by the OABq Questionnaire. This objective will be assessed in subjects with OABq data at baseline and after 12th PTNM therapy session.

Endpoint definition

OABq Questionnaire collected from baseline and the 12th PTNM therapy session will be used for analysis of this objective.

Data collection and analysis methods

OABq Questionnaire collected from baseline and the 12th PTNM therapy session will be used for analysis of this objective. OABq consists a symptom bother scale and four health related quality of life (HRQL) subscales (Coping, Concern, Sleep and Social interaction). They will be scored according to published scoring criteria². Symptom bother scale and 4 HRQL subscales are measured as 0-100 using a range percentile transformation on the summed value from individual listed items. The HRQL score is a calculated score with a range from 0 to 100 using a range percentile transformation on the summed value from 4 subscales (Coping, Concern, Sleep and Social interaction). For the subscale analyses, if $< 50\%$ of the scale items are missing, the scale should be retained with the mean scale score of the items present used to impute a score for the missing items. If $\geq 50\%$ of the items are missing, no scale score

should be calculated, the subscale score should be considered missing. If a subscale score is missing, the HRQL Total score cannot be calculated. These scores will be analyzed for changes from baseline to the 12th PTNM. Calculation of change from baseline will be computed subtracting baseline values from the 12th PTNM values. A paired t-test or the Wilcoxon signed-rank test will be used to evaluate the changes after the 12th PTNM therapy session from baseline after testing for data normality by calculating Shapiro-Wilk W statistic.

Determination of subjects for analysis

This objective will be assessed in all qualified subjects who receive PTNM therapy and have OABq questionnaire data available at both baseline and the 12th PTNM session.

In addition to the primary analysis which includes subjects with diary data from baseline and 12th PTNM therapy session, the same sensitivity analyses as described in primary objective will be performed for secondary objective #2.

Improvement in OABq from baseline will also be summarized at by the PTNM session (session #1, #4, #8 and #12) when this data is collected.

7.9.3. Additional Measures

7.9.3.1. Incidence of device-related or therapy/procedure-related adverse events

Objective:

To summarize the device-related or therapy/procedure-related adverse events for all subjects who receive the PTNM therapy.

Endpoint definition

Device-related and therapy/procedure-related adverse events are defined as possible, probable and causal relationship to study procedure, NURO external neurostimulator, therapy session kit, and stimulation as reported on the event case report form (CRF). The sponsor assessment on the event is documented in the Medtronic Use Only CRFs. When there are differences in event CRF reporting and MUO CRFs, both will be reported in the final report, and the events summaries will be based on more conservative approach: for example, if it is reported as device related and not assessed as such in MUO CRF, the event will be counted as device related in event summaries.

Data collection and analysis methods

Device-related and therapy/procedure-related adverse events will be summarized by MedDRA preferred terms for all qualified subjects who receive the PTNM therapy. Number of subjects and percent of

subjects in each preferred term will be reported. These events will be further summarized by serious events and non-serious events.

Determination of subjects for analysis

All qualified subjects who receive the PTNM therapy will be included in the analysis.

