14.5. Additional Measures

Additional measures include:

- Incidence of device-related and therapy-related adverse events
- Nocturia / Nighttime voiding frequency
- Urgency including the Urgency Perception Scale (UPS)
- Patient-reported Outcomes:
 - Self-Assessment Goal Achievement Questionnaire (SAGA)
 - Patient Perception of Bladder Condition (PPBC)
 - Patient Global Impression of Improvement (PGI-I)

Nocturia, nighttime voiding frequency and urgency are collected through voiding diaries and patient reported outcomes. Reductions in nocturia, nighttime voiding frequency and urgency from baseline will be summarized by the PTNM session when the data is collected.

Additional quality of life measures including PPBC, UPS, PGI-I and SAGA are collected in this study. These data will be summarized by the PTNM session when data is collected.

Confidential

Reportable adverse events will be summarized for all subjects who receive the therapy.

Fecal incontinence diaries will be collected for subjects with dual incontinence. No analysis is pre-specified for dual incontinence data. The intent of collecting this information is to inform future study designs.

15. Ethics

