7.10. Safety Evaluation

In the study, reportable Adverse Events are collected. All serious, device related, therapy/procedure related and all device deficiencies are considered as reportable for this study. The sponsor assessment is documented in the Medtronic Use Only (MUO) CRFs. When there are differences in event CRF reporting and MUO CRFs, both will be reported in the final report, and the events summaries will be based on more conservative approach: for example, if it is reported as device related and not assessed as such in MUO CRF, the event will be counted as device related in event summaries.

Incidence of device-related and therapy/procedure-related adverse events will be summarized as detailed in Section [7.9.3](#).

Serious AEs (SAEs), regardless of device-related, therapy/procedure-related or not, will also be summarized for all enrolled subjects.

Device Deficiency will be summarized for qualified subjects who receive PTNM therapy. Additionally, Narratives of SADEs (Serious Adverse Device Effects) will be provided.

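### The SAP restricts the related-adverse-event and device-deficiency summaries to eligible treated subjects, where the protocol says all treated subjects, and declares no change

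*SAP*

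**What the plan says.** Protocol 14.5 sets the safety population: "Reportable adverse events will be summarized for all subjects who receive the therapy". The protocol glossary and sections 12.1 and 12.2 class every device deficiency as reportable.

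SAP 7.9.3.1 opens with the same population. Its objective is to summarise "device-related or therapy/procedure-related adverse events for all subjects who receive the PTNM therapy". Two later paragraphs of that section are narrower:

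- Methods: "adverse events will be summarized by MedDRA preferred terms for all qualified subjects who receive the PTNM therapy", followed by "These events will be further summarized by serious events and non-serious events".
- Determination of subjects: "All qualified subjects who receive the PTNM therapy will be included in the analysis".

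SAP 7.10 has three rules:

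- Device deficiencies: "Device Deficiency will be summarized for qualified subjects who receive PTNM therapy".
- Serious adverse events: "will also be summarized for all enrolled subjects".
- Narratives: "Narratives of SADEs (Serious Adverse Device Effects) will be provided", with no analysis set named.

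SAP 7.1.3 defines *qualified*, for the whole document, as meeting the inclusion and exclusion criteria. SAP 7.11 states that the planned analyses do not differ from the protocol.

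**The concern.** A safety summary for a device should count everyone exposed to it. Under the SAP's definition, a subject who received sessions and is later found to have breached a criterion leaves both the numerator and the denominator of the related-event table, and leaves the device-deficiency summary.

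Such a subject may be one of particular interest. Several exclusion criteria are also device contraindications in Protocol 11.1.3 (proneness to bleeding, relevant nerve damage, pacemakers or defibrillators, pregnancy), and needle-site bleeding and toe numbness are among the known risks in Protocol 11.1.1.

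At stake are non-serious related events and device deficiencies, which have no other planned summary. A serious related event would still appear among the SAEs, but could be absent from the table meant to show related events.

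**Working it through.** **Comparison of the texts.** The documents give no figure that tests this point, so the check starts with the populations.

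| Output | Population | Source |
|---|---|---|
| Reportable events, including deficiencies by definition | All treated | Protocol 14.5, with glossary, 12.1, 12.2 |
| Related events, objective | All treated | SAP 7.9.3.1 |
| Related events, methods and determination | Eligible and treated | SAP 7.9.3.1 with 7.1.3 |
| Serious/non-serious split of related events | Eligible and treated | SAP 7.9.3.1 |
| Device deficiencies | Eligible and treated | SAP 7.10 |
| SAEs | All enrolled | SAP 7.10 |
| SADE narratives | None stated | SAP 7.10 |

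The SAP contradicts its own objective within 7.9.3.1 and departs from Protocol 14.5. A serious device effect in a treated subject in breach would count as an SAE, and would have a narrative if no restriction is read into that sentence, yet would not be in the related-event table.

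**Can the two sets differ?** Protocol 7.1 exits non-qualifiers found before Session #1, so with perfect screening they coincide. They differ if someone is treated in breach. Protocol 10.10 lists violation of, or change in, eligibility criteria as an exit reason, and SAP 7.6 treats being qualified and being treated as two separate conditions.

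**Illustration of size.** No breach count or event rate is given, so these inputs are assumptions: N = 120 treated, E = 12 with a related event (10.0%), and k = 1, 3 or 6 in breach, independently of events. The number of event subjects dropped is then hypergeometric.

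- Expected number dropped = kE/N: 12/120 = 0.1, 36/120 = 0.3, 72/120 = 0.6.
- P(at least one dropped) = 1 − C(108,k)/C(120,k): 0.100, 0.273, 0.476. For k = 3, this is 1 − (108·107·106)/(120·119·118) = 1 − 0.727.
- P(two or more dropped): 0, 0.026, 0.110.
- Expected table percentage = (12 − 12k/120)/(120 − k) = 12/120 = 10.0% for every k.
- With k = 6, dropping 0, 1 or 2 event subjects gives 12/114 = 10.5%, 11/114 = 9.6% or 10/114 = 8.8%.
- An event or deficiency seen in only one subject disappears with probability k/120: 0.8%, 2.5%, 5.0%.

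P(at least one dropped) for other event counts:

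| Event subjects | k = 1 | k = 3 | k = 6 |
|---|---|---|---|
| 6 | 5% | 14% | 27% |
| 12 | 10% | 27% | 48% |
| 24 | 20% | 49% | 75% |

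With k = 0 the effect is nil.

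**A related ambiguity.** Inclusion criterion 2 (Protocol synopsis and 9.3, SAP 5.3) counts urgency episodes on the diary. Protocol 10, 10.6 and 10.10 refer to UUI episodes. A subject with three urgent voids and no leak meets the diary part of the listed criterion but must be exited under section 10, so *qualified* itself has two readings.

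**The case against.** The strongest reply is that *qualified* only marks subjects who passed the pre-treatment gate. Enrolment means signed consent, so a word is needed to separate screen failures, and both Protocol 7.1 and SAP 5.5 place qualification before the first session. On that reading every treated subject is qualified and nothing is lost. The reading is possible, but it is not the definition in SAP 7.1.3, and it would make the word redundant beside *who receive the therapy*. Deleting it would then cost nothing.

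Several further points stand in part:

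- The exit reason in Protocol 10.10 does not distinguish before from after treatment, so it shows that violations are contemplated, not that treated breaches are expected.
- SAEs in all enrolled subjects alongside related events in treated subjects is a coherent choice, since SAEs can precede treatment. Only the eligibility limit is at fault.
- Protocol 14.5 does not name device deficiencies. The conflict there runs through the definition of reportable events, and other protocol passages list events and deficiencies as separate items.
- The unrestricted status of the narratives is inferred from silence.
- The probabilities rest wholly on assumed inputs.

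Review of every reported event by the sponsor's medical monitor (Protocol 13) and the deviation summary by type (SAP 7.1.2) do not put a dropped event back into a summary.

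**Conclusion.** The concern holds, and the SAP is wrong as written. Its defined term gives a narrower safety set than Protocol 14.5 and than the objective of SAP 7.9.3.1, and SAP 7.11 does not declare it. It should be fixed before analysis.

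The practical size is modest. The number affected may be zero, SAEs remain covered, and no efficacy result or sample size changes. Under the assumptions above the expected event rate does not move; what can be lost is individual events, and that matters most for a term reported in one subject. If breaches of criteria that are also contraindications raise event risk, independence fails and the loss would be larger than shown.

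The urgency/UUI conflict is a separate, minor point on which this conclusion does not depend. It has about nil effect on the primary analysis while the section 10 check is enforced.

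**What to change.** Delete *qualified* in three places: the methods paragraph of SAP 7.9.3.1, its determination-of-subjects paragraph, and the device-deficiency sentence of SAP 7.10. Both summaries then cover every subject who received at least one PTNM session. The cost is a small SAP edit, with no new data, no new analysis and no protocol amendment. Keeping the restriction and declaring it with reasons in SAP 7.11 would cure the undeclared change, but not the loss of events.

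Separately, reconcile inclusion criterion 2 (Protocol synopsis and 9.3, SAP 5.3) with Protocol 10, 10.6 and 10.10 so that one diary rule applies. Which rule is right is for the sponsor to decide. Any change to protocol wording follows Protocol 16.6, which requires IRB approval before implementation unless the change is purely administrative or logistical. SAP 5.3 would be aligned with it. No additional primary analysis is needed.

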7.9.3.2. Nocturia/ Nighttime voiding frequency

Objective:

To summarize the reductions in nocturia and nighttime voiding frequency from baseline by PTNM session when data is collected.

Endpoint definition

Nocturia is measured as the number of times the subject is woken from sleep to void. Nighttime frequency is measured as number of voids during nighttime sleep.

Data collection and analysis methods

Nighttime voiding and nocturia are collected on diaries for baseline visit, 1st, 4th, 8th and 12th PTNM sessions. Reduction in average night time voids per day and nocturia per day will be calculated for each subject from baseline to each PTNM session when diary data is collected. Average night time voids per day will be calculated by summing all reported night time voids and dividing by the total number of days of diaries. Average nocturia per day will be calculated by summing all reported nocturia episodes and dividing by the total number of days of diaries. For a diary to be included in the analysis, it needs to have complete leak and/or void episode entries for at least one day. For any reported episode if leak or void is not indicated, the diary of that day will not be included.

Determination of subjects for analysis

Reduction of nocturia and nighttime voiding frequency from baseline will be calculated for all qualified subjects who receive PTNM therapy and report baseline nighttime voiding and nocturia data respectively.

7.9.3.3. Urgency including the Urgency Perception Scale (UPS)

Objective:

To summarize UPS at baseline and by PTNM sessions for subjects who receive PTNM therapy.

Endpoint definition:

UPS is a three-category scale to measure the urgency perceptions based on subjects' experience when they have a desire to urinate.

Data collection and analysis methods:

UPS data are collected for baseline and the 1st, 4th, 8th and 12th PTNM sessions. Number of subjects and percent of subjects in each category of the scale will be summarized by visit.

As an additional analysis to look at urgency besides UPS, urgency is also collected for diary episodes such as no urgency, mild, moderate and severe. The following scores will be assigned to each urgency degree: 0= no urgency; 1=mild; 2=moderate; 3=severe. Average urgency score will be calculated by summing urgency scores for leaking episodes and dividing by the total number of leaks in 3-day voiding diary when urgency is reported. Average urgency score will be reported at baseline and 1st, 4th, 8th and 12th PTNM sessions. For a diary to be included in the analysis, it needs to have complete leak and/or void episode entries for at least one day. For any reported episode if leak or void is not indicated, the diary of that day will not be included.

Determination of subjects for analysis:

All qualified subjects who receive PTNM therapy and have data available will be included in the analysis.

7.9.3.4. Patient reported outcomes

- Self-Assessment Goal Achievement Questionnaire (SAGA)

Objective:

To summarize SAGA first visit at baseline and SAGA follow-up collected at final visit after 12th PTNM session for subjects who receive PTNM therapy.

Endpoint definition:

The SAGA questionnaire asks subjects to rank, in order of importance for standard urology symptom goals using a scale of 0-5 and allows for other personal goals to be included³. In SAGA follow-up assessment, it includes a scale of -2 to 2 to report on achievement of each symptom goal and other personal goal(s). The questionnaire includes an assessment question of "Overall, to what extent have you achieved your goals" on a scale of 0-4.

Data collection and analysis methods:

SAGA data are collected for baseline (goal-assessment; ranking) and follow-up (goal-achievement) after the 12th session.

SAGA data will be analyzed for subjects who receive the PTNM therapy and have data at baseline and follow-up after the 12th session. Baseline data will be summarized by importance of symptom goals for

each fixed symptom goal. Number of subjects and percent of subjects in each rating from not very important to very important for each fixed goal will be reported.

In the SAGA follow-up, SAGA goal achievement for each fixed goal will be tabulated from much worse than expected to much better than expected. The assessment on overall question on goal achievement will be summarized from “Did not achieve my goals at all” to “Exceeded my goals”.

For the SAGA follow-up, goal attainment scores will be calculated according to the formula provided by Kiresuk and Sherman⁴ (T-scores with mean=50 and SD=10) for 9 fixed goals. Additionally, weights will be applied to goal achievement ratings based on the baseline level of importance attached to each goal. Descriptive statistics for the T-scores will be reported. A mean T-score of 50 represents an outcome of goal achievement. Scores>50 are interpreted as exceeding goal and scores <50 as only somewhat or partially achieving goal⁵.

Determination of subjects for analysis:

All qualified subjects who receive PTNM therapy with both SAGA first and SAGA follow-up data will be included in the analysis.

- Patient Perception of Bladder Condition (PPBC)

Objective:

To summarize PPBC at baseline and by PTNM sessions for subjects who receive PTNM therapy.

Endpoint definition

PPBC is a 6-point scale to describe the subject's bladder condition from bladder condition not causing problem to causing many severe problems.

Data collection and analysis methods

PPBC data are collected for baseline and the 1st, 4th, 8th and 12th PTNM sessions. Number of subjects and percent of subjects in each condition of the scale will be summarized by visit.

Determination of subjects for analysis

All subjects who are treated by the PTNM therapy and have data available will be included in this analysis.

- Patient Global Impression of Improvement (PGI-I)

Objective:

To summarize PGI-I collected at the end of the study.

Endpoint definition

PGI-I is a single question asking the patient to rate their urinary condition as compared with prior to beginning treatment on a scale from 1 (very much better) to 7 (very much worse).

Data collection and analysis methods

This questionnaire is collected following the 12th PTNM session. Number of subjects and percent of subjects in each of 7 categories will be presented for subjects with data available, especially the number and percent of subjects who report “Very much better” and “Much better” will be provided.

Furthermore, three categories with “Very much better” and “Much better”, “A little better” combining into “Better”; “No change” as “Same”; and “A little worse”, “Much worse”, and “Very much worse” combining into “Worse” will be analyzed. Additionally, descriptive statistics including mean, standard deviation, and median will be provided.

Determination of subjects for analysis

All qualified subjects who receive PTNM therapy and have data available will be included in this analysis.

7.10. Safety Evaluation

In the study, reportable Adverse Events are collected. All serious, device related, therapy/procedure related and all device deficiencies are considered as reportable for this study. The sponsor assessment is documented in the Medtronic Use Only (MUO) CRFs. When there are differences in event CRF reporting and MUO CRFs, both will be reported in the final report, and the events summaries will be based on more conservative approach: for example, if it is reported as device related and not assessed as such in MUO CRF, the event will be counted as device related in event summaries.

Incidence of device-related and therapy/procedure-related adverse events will be summarized as detailed in Section [7.9.3](#).

Serious AEs (SAEs), regardless of device-related, therapy/procedure-related or not, will also be summarized for all enrolled subjects.

Device Deficiency will be summarized for qualified subjects who receive PTNM therapy. Additionally, Narratives of SADEs (Serious Adverse Device Effects) will be provided.

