12.1. Definitions/Classifications

Any adverse event meeting the definition of: serious, device related, and/or procedure related as well as all device deficiencies will be considered reportable for this study. Adverse events and device deficiencies are defined as follows:

Term	General
Adverse Event (AE)	Any untoward medical occurrence, unintended disease or injury, or untoward clinical signs (including abnormal laboratory findings) in subjects, users or other persons, whether or not related to the medical device under investigation.
Adverse Device Effect (ADE)*	Adverse event related to the use of the medical device under investigation.
Device Deficiency (DD)*	Inadequacy of a medical device with respect to its identity, quality, durability, reliability, safety or performance. Device deficiencies include malfunctions, misuse or use errors, and inadequate labeling. 
▪ Malfunctions: Failure of the medical device under investigation to perform in accordance with its intended purpose when used in accordance with the instructions for use or Clinical Investigational Plan (CIP)▪ Use Error: Act or omission of an act that results in a different medical device response than intended by the manufacturer or expected by the user

Confidential

SERIOUSNESS	
Serious Adverse Event (SAE)*	
An adverse event that
 
 a) led to a death, b) led to a serious deterioration in the health of the subject, that either resulted in: 
 1. a life-threatening illness or injury, or 2. a permanent impairment of a body structure or a body function, or 3. in-patient or prolonged hospitalization, or 4. medical or surgical intervention to prevent life threatening illness or injury or permanent impairment to a body structure or a body function. c) led to fetal distress, foetal death or a congenital abnormality or birth defect. 
Note: A planned hospitalization for pre-existing condition, or a procedure required by the CIP, without a serious deterioration in health, is not considered to be a serious adverse event.

Serious Adverse Device Effect (SADE)*	Adverse device effect that resulted in any of the consequences characteristic of a serious adverse event
Unexpected Serious Adverse Device Effect (USADE)*	Serious adverse device effect which by its nature, incidence, severity or outcome has not been identified.
RELATEDNESS	

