Relationship of Adverse Events	
The relationship of the adverse event to the study treatment (device, therapy) will be described using the following terms:
 
 • Not related • Unlikely • Possible • Probable • Causal relationship

*Reportable event categories that will be collected during this study

Confidential

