12.2. Reporting of Adverse Events

Any adverse event meeting the definition of serious, device related, and/or procedure related as well as all device deficiencies as defined in above will be considered reportable for this study. The procedure is defined as each PTNM therapy session.

Worsening of OAB symptoms will be collected as part of the efficacy measures and are not considered a reportable adverse event.

All reportable adverse events will be classified using the following responsibility matrix:

Event Classification Responsibilities

What is Classified	Who Classifies	Classification Parameters
Relatedness	Investigator	Procedure related Device related Other
USADE potential	Medtronic	USADE
Seriousness	Investigator	SAE/SADE
Diagnosis	Investigator	Based on presenting signs and symptoms and other supporting data
	Medtronic	MedDRA term assigned based on the data provided by investigator

All reportable adverse events must be recorded in the subject's medical record and on the Adverse Event and/or Device Deficiency eCRF and promptly reported to Medtronic. IRB reporting must be completed in accordance with the policies of the governing IRB.

Reports of adverse events and device deficiencies will include the following information, at a minimum:

- Date of event
- Diagnosis or description of the event
- Assessment of the seriousness and relationship to the product(s) under study
- Treatment
- Outcome and date or resolution

It is the responsibility of the Investigator to identify the occurrence of reportable adverse events and device deficiencies and to ensure the required information is accurately documented on the eCRF.

The clinical course of each adverse event must be followed until resolution or subject discontinuation from the study, whichever comes first. "Ongoing" adverse events and device deficiencies must be assessed at each protocol required visit, and new or updated information must be documented on the Adverse Event and Device Deficiency eCRF and promptly reported to Medtronic and if applicable to the IRB.

If necessary, the Investigator may report to the sponsor initially by telephone or email and follow-up with completed eCRFs and, if possible, copies of source documentation regarding the event (e.g., physician/nurse notes or summaries).

Medtronic study personnel will promptly review all reported adverse events and device deficiencies and if necessary request clarification and/or additional information from the Investigator. If Medtronic

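### SAP 7.10 summarises device deficiencies only for qualified, treated subjects, so some deficiencies that the protocol makes reportable have no planned deficiency output

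*SAP*

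**What the plan says.** **What is reportable.** Protocol 12.1 defines an adverse event as an untoward occurrence "in subjects, users or other persons, whether or not related to the medical device under investigation". An adverse device effect is an "Adverse event related to the use of the medical device under investigation", so it inherits that scope. Adverse device effects and device deficiencies both carry the asterisk that the footnote explains as "Reportable event categories that will be collected during this study". The opening sentence of 12.1 ends "as well as all device deficiencies will be considered reportable for this study", and asks for no link to a treated subject. SAP 7.10 repeats this: "All serious, device related, therapy/procedure related and all device deficiencies are considered as reportable for this study".

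**How it is recorded.** Protocol 12.2: "All reportable adverse events must be recorded in the subject's medical record and on the Adverse Event and/or Device Deficiency eCRF".

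**What is reported.** The SAP plans four safety outputs:

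- Related adverse events (7.9.3.1), for qualified subjects who receive the therapy.
- Serious adverse events (7.10), for all enrolled subjects.
- Device deficiencies (7.10): "Device Deficiency will be summarized for qualified subjects who receive PTNM therapy".
- Narratives of serious adverse device effects (7.10), with no population stated.

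SAP 7.1.3 defines qualified subjects as those who satisfy the eligibility criteria. Protocol 14.5 summarises reportable adverse events over all subjects who receive the therapy.

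**The concern.** The plan collects a wider class of events than it reports. For deficiencies, this is a stated rule and not just missing detail: inclusion depends on therapy having been received. Protocol 12.1 counts malfunctions and use errors as deficiencies, and protocol 8.1 requires the device to be activated and sessions to be downloaded and transferred before use. A fault at that stage can occur before any therapy, and if the subject never receives a session, the fault itself removes the event from the summary.

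The protocol synopsis rests the safety evaluation on reportable adverse events and device deficiencies. There is no events or data monitoring committee (protocol 13) and no product accountability (protocol 8.5). A reader of the final report would probably take the deficiency table as complete. It could show none of the excluded kinds when some had been reported.

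**Working it through.** The plan states no figure on this point, so the check is to match each kind of reportable event with the SAP output that would carry it.

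| Reported event | Reportable under protocol 12.1? | Planned SAP output |
|---|---|---|
| Deficiency, qualified subject with at least one session | Yes | Deficiency summary (7.10) |
| Deficiency, treated subject later found not qualified | Yes | No deficiency output |
| Deficiency, qualified subject who never receives a session | Yes | No deficiency output |
| Deficiency not linked to any subject (e.g. found at set-up) | Yes | No deficiency output |
| Non-serious adverse device effect in a user or other person | Yes, through the adverse event definition | None |
| Serious adverse device effect in a user or other person | Yes, on the same basis | No table; possibly the narratives, whose scope is unstated |
| Serious adverse event in any enrolled subject, treated or not | Yes | Serious event summary (7.10) |

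**Notes on the rows.**

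1. The deficiency population is defined by subject, not by session. A failed attempt at Session #1 followed by any delivered session belongs to a subject who receives therapy. So does a failure at Sessions #2 to #12 in a subject already treated. Both are counted if the subject is qualified. SAP 7.7 expects that more than one attempt may be needed at a visit.
2. If an excluded deficiency leads to a serious adverse event in an enrolled subject, that event reaches the serious event summary. The deficiency itself still has no deficiency output.
3. The SAP treats its safety categories differently: serious events are counted whether or not therapy was given, deficiencies are not.

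**Illustration of the mechanism only.** The documents give no deficiency rate. Assume that *k* of the maximum 120 qualified subjects never receive a session because the device failed:

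- *k* = 1: the table shows 0/119 for these events, against 1/120 = 0.8%.
- *k* = 2: the table shows 0/118, against 2/120 = 1.7%.

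Nothing in the documents makes either value likely. A second attempt may well succeed, and the subject would then be counted.

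**The case against.** The strongest defence is that the protocol itself works on subjects and the SAP follows it.

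- Protocol 10.7 assesses subjects for reportable events, and 12.2 ties recording to the subject's chart. Users and other persons appear only in a general definition.
- The protocol glossary includes device deficiencies in its entry for reportable adverse events. Protocol 14.5 can therefore be read as already limiting deficiencies to subjects who receive the therapy.
- Incidence needs a subject denominator, and treated subjects are the usual choice.
- Excluded events are not lost to oversight. The medical monitor reviews all reported events and deficiencies (protocol 13), and the study is conducted under medical device reporting rules (protocol 5 and 15.1).
- A subject who leaves untreated after a device failure would appear in disposition, with a reason (SAP 7.1.1; protocol 10.10).

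Much of this stands. The subject-only framing begins in the protocol, the user-event part is minor, and treated subjects are a sound denominator for an incidence table. It does not supply an output. Monitor review and disposition reasons are not a deficiency summary. The glossary reading explains at most the treated condition. The qualified condition is added by the SAP, although SAP 7.11 reports no changes from the protocol.

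A reader might infer more from these passages. Three stronger readings are not supported:

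- *That these events can never reach the safety results.* The narratives carry no subject restriction, and serious events in untreated enrolled subjects are tabulated.
- *That failures to deliver therapy are dropped in general.* Among qualified subjects, only failures in those who never receive a session fall out.
- *That the number of missed operator injuries can be estimated.* The schedule allows at most 120 × 12 = 1,440 sessions, but the documents give no injury rate to apply to them.

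**Conclusion.** The point holds as a reporting gap of limited size. Protocol 12.1 and SAP 7.10 make every device deficiency reportable, while SAP 7.10 leaves three kinds without a deficiency output: those with no linked subject, those in treated but unqualified subjects, and those in qualified subjects who never receive a session. Non-serious adverse device effects in users or other persons have none either. The scope of the narratives is unstated, so coverage of serious ones is uncertain.

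Few such events are to be expected with a commercially released device and subject-based collection. That is a judgement, since no rate can be derived from the documents. The primary and secondary efficacy analyses are untouched. The conclusion assumes that SAP 7.10 is applied as written and that the adverse device effect definition inherits the persons named in the adverse event definition. The deficiency part does not need the second assumption. The change is still worth making, because the rule makes a measure of device reliability depend on therapy having been delivered, and it is easily repaired.

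**What to change.** 1. **SAP 7.10, deficiencies.** Replace the sentence with a commitment to count and list all reported device deficiencies, whether or not therapy was delivered and whether or not a subject is linked. Keep any subject-based incidence table separate, with its population stated. A plain count is enough: a sessions-attempted denominator would not fit faults found outside a session, and the documents do not say that attempts are recorded.
2. **SAP 7.10, users and other persons.** List any adverse device effects in non-subjects apart from the subject tables, and state that the narratives of serious adverse device effects cover them. Protocol 12.2 should then allow these events on the eCRF without an entry in a subject's chart.
3. **Alternative to item 2.** If safety is meant to cover subjects only, reconcile the adverse event definition in protocol 12.1 with the subject-only text in 12.2 and 14.5.
4. **SAP 7.11.** Note the change, since protocol 14.5 can be read as limiting the summary to treated subjects.

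The cost is a few sentences and one extra listing, with no added visits.
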